7.3.3. Urinalysis

Urinalysis will include testing for the following:

- protein
- glucose
- ketones

- blood (hemoglobin)
- pH
- specific gravity
- microscopic
 - bacteria
 - RBCs
 - WBCs
 - casts
 - crystals

7.3.4. Other Clinical Laboratory Tests

7.3.4.1. Human Chorionic Gonadotropin Tests

Serum human chorionic gonadotropin (HCG) tests will be performed for all women at screening (visit 1). Urine HCG tests will be performed for all women of childbearing potential at all subsequent visits, and if clinically indicated thereafter. Any patient who becomes pregnant during the study will be withdrawn. Procedures for reporting the pregnancy are provided in Section 7.2.

7.4. Vital Signs

Vital signs [pulse, blood pressure (supine and standing), and body temperature] will be measured at the time points detailed in Table 1.

Before pulse and blood pressure are measured, the patient must be in a supine or sitting position and resting for at least 5 minutes. (The same position and arm should be used each time vital signs are measured for a given patient.) For any abnormal vital sign finding, the measurement should be repeated as soon as possible. Any vital sign value that is judged by the investigator as a potentially clinically significant change (worsening) from a baseline value will be considered an adverse event, recorded on the source documentation and transcribed onto the CRF, and monitored as described in Section 7.1.2.

7.5. Electrocardiography

A 12-lead ECG will be conducted at every visit, at the time points detailed in Table 1. ECGs will be performed in triplicate at screening, and a single measurement performed at all subsequent visits.

A qualified physician at a central diagnostic center will be responsible for interpreting the ECG. Any ECG finding that is judged by the investigator as a potentially clinically significant change (worsening) compared with a baseline value will be considered an adverse event, recorded on the source documentation and transcribed onto the CRF, and monitored as described in Section 7.1.2.

7.6. Physical Examinations

Physical examinations and weight will be performed at the time points detailed in [Table 1](#).

The brief (symptom-directed) physical exam will be focused on general appearance, the cardiovascular, pulmonary, abdominal exams, as well as directed towards any patient-reported symptoms. The brief neurological exam includes observation for cerebellar (intention) tremor and for non-cerebellar tremors (eg, resting or positional), finger-nose, heel-shin, Romberg, tandem walking, positional, and gaze-evoked nystagmus.

Any physical examination finding that is judged by the investigator as a potentially clinically significant change (worsening) compared with a baseline value will be considered an adverse event, recorded on the CRF, and monitored as described in [Section 7.1.2](#).

7.7. Concomitant Therapy or Medication

Concomitant therapy or medication usage will be monitored throughout the study. Details of prohibited medications are found in [Section 5.3](#). As part of the additional implemented monitoring procedures, information regarding changes in use of benzodiazepines and antidepressants will be collected in inquiries about concomitant medication. Inquiries about changes in use of alcohol and illicit drugs will also be conducted. The information collected as part of the safety monitoring, together with the C-SSRS and the PBA-s, will be verified with the patient's caregiver, spouse or other support person (where necessary)².

7.8. Other Safety Measures and Variables

7.8.1. Columbia Suicide Severity Rating Scale

The C-SSRS will be used to rate the patient's degree of suicidal ideation on a scale ranging from "no suicidal ideation" to "active suicidal ideation with specific plan and intent" ([Posner et al 2011](#)). The C-SSRS Baseline version will be completed at screening (Visit 0), while the C-SSRS Since Last Visit version will be completed at the time points detailed in [Table 1](#). Patients with active suicidal ideation, as measured by a score of 4 or 5 on the C-SSRS at the screening visit, will not be eligible for the study.

In any event of suspected active suicidality (e.g. active suicidal ideation or intent, significant suicidal behavior) or clinical findings suggesting that the patient is dangerous to himself or herself, the patient should be referred for **immediate** psychiatric evaluation.

Patients with a positive C-SSRS suicidal ideation score of 1 and 2 will be monitored more closely and treated according to the investigator's medical judgment. Patients with C-SSRS or PBA-s suicidality scores 1 and 2 may be handled by study investigator/neurologist with a consultancy with psychiatrists where necessary per investigator's medical judgement.

Patients with C-SSRS or PBA-s suicidal ideation >2 (ie, 3, 4, 5), and all patients with C-SSRS suicidal acts, will be discontinued from treatment with study medication. A referral for psychiatric evaluation is required for AE/SAE of suicidal ideation/suicidal attempt or significant

² In accordance with the American Psychiatric Association's 2003 Practice Guideline for the Assessment and Treatment of Patients with Suicidal Behaviors.

increase in the suicidality scale from baseline (e.g., 2 point increase or higher) or C-SSRS or PBA-s suicidality score 3 and above.

Patients who are discontinued from treatment may continue their participation in the study and perform the scheduled visits and assessments, while off study drug. They will continue to be closely monitored by the investigator and will be referred for psychiatric evaluation per the investigator's medical judgment.

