- ^l If less than 3 months have passed since the patient's completion of the PRIDE-HD protocol and the Open-PRIDE screening visit, the "since last visit" version of the scale can be used. If 3-6 months have passed, the screening/baseline version of the scale should be administered.
- ^m The "Since Last Visit" version will be administered at all subsequent visits.
- ⁿ The safety telephone calls will include an abbreviated PBA-s (a subset of PBA-s questions on depressed mood, suicidal ideation, anxiety, irritability, loss of motivation, and obsessive-compulsive behaviors).
- ^o Including digitomotography (speeded index finger tapping), dysdiadochomotography (pronation/supination hand tapping), manumotography and choreomotography (grip force and chorea analysis) and pedomotography (speeded foot tapping).
- ^p PK samples will be aimed to be drawn, to the extent possible, in the event of a SAE, an AE leading to discontinuation, or for patients who withdrew prematurely because of lack of efficacy.
- ^q At the end-of-treatment (EoT) visit (Visit 8), study drug will only be collected.
- ^r Patients will undergo a 1-week titration in which a pridopidine dose of 22.5 mg bid (total daily dose 45 mg) will be taken. From week 2 onwards, patients will receive a pridopidine dose of 45 mg bid (total daily dose 90 mg). Doses up to 112.5 mg bid are currently being investigated in the ongoing PRIDE-HD study. Following availability of PRIDE-HD results, the dose administered in this study may be adjusted.
- ^s This information will be collected as part of concomitant medication inquiry.
- ^t Study adherence will be reviewed during the safety telephone calls.

Abbreviations: bid=twice daily; β -HCG=beta human chorionic gonadotropin ; C-SSRS=Columbia-Suicide Severity Rating Scale; ET=Early Termination; mPPT=Modified Physical Performance Test; PBA-s=Problem Behaviors Assessment-Short form; PK=pharmacokinetic(s); Q26=every 26 weeks after the Month 12 visit; TC=telephone contact; TFC=Total Functional Capacity; TMS=Total Motor Score; SAE=serious adverse event; SF-12=Short Form 12; Q-motor=Quantitative motor; UHDRS=Unified Huntington's Disease Rating Scale; V=Visit

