- serum β -HCG test for women of childbearing potential

- C-SSRS
 - If less than 3 months have passed between the patient's completion of the PRIDE-HD study and the Open-PRIDE screening visit, the "Since Last Visit" version of the scale may be administered.
 - If the gap is between 3-6 months, the screening/baseline version of the scale will be administered.
- UHDRS-TMS
- PBA-s
- inquire about AEs
- concomitant medication inquiry (including inquiry about changes in use of benzodiazepines and antidepressants)
- inquiry about changes in use of alcohol and illicit drugs
- inform patients of study restrictions and compliance requirements

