- g. Creatinine clearance <60 mL/min at screening, calculated using the Cockcroft-Gault equation: $(140 - \text{age}) \times \text{mass (kg)} \times [0.85 \text{ if female}] / 72 \times \text{serum creatinine (mg/ dL)}$. It is allowed to repeat the test once, if clinically appropriate.
- h. Any clinically significant, abnormal, screening laboratory result which in the opinion of the investigator, affects the patients' suitability for the study or puts the patient at risk if he/she enters the study.

- i. [Revision 1] Patients with adverse events of suicidal ideation or attempt at any time in the past or as measured by suicide ideation score of ≥ 3 on the C-SSRS, or PBA-s or patients who answer “Yes” on any of the 5 C-SSRS Suicidal Behavior Items (actual attempt, interrupted attempt, aborted attempt, preparatory acts, or behavior) if the attempt or acts were performed at any time in the past, or patients who, in the opinion of the investigator, present a risk of suicide.
- j. Females who are pregnant or breastfeeding.
- k. Treatment with any investigational product other than pridopidine within 6 weeks of screening or patients planning to participate in another clinical study assessing any investigational product during the study.

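### The C-SSRS entry rule is stated inconsistently: exclusion criterion i and Protocol 7.8.1 differ at an ideation score of 3, and 7.8.1 disagrees with Table 1 and 3.12.1 on which form is used at screening

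*Protocol*

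**What the plan says.** **Threshold.** Protocol 4.2, criterion i, excludes patients with suicidality "as measured by suicide ideation score of ≥ 3 on the C-SSRS, or PBA-s". The synopsis repeats it. Protocol 7.8.1 states the entry bar differently: patients with active ideation, "as measured by a score of 4 or 5 on the C-SSRS at the screening visit, will not be eligible for the study". After entry, Protocol 3.10.1 and 7.8.1 itself both discontinue patients whose C-SSRS ideation score is above 2.

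**Past behaviour.** Criterion i also excludes a positive answer on any of the five C-SSRS behaviour items "if the attempt or acts were performed at any time in the past". Section 7.8.1 names no behaviour item as a bar to entry.

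**Form.** Section 7.8.1 states: "The C-SSRS Baseline version will be completed at screening (Visit 0") (screening is Visit 1 everywhere else). Table 1 footnote l sets a condition, "If less than 3 months have passed since the patient's completion of the PRIDE-HD protocol and the Open-PRIDE screening visit", under which the Since Last Visit version is allowed. Section 3.12.1 likewise says that this "version of the scale may be administered". Both call for the screening/baseline version when the gap is 3 to 6 months. Visit 2 uses the Since Last Visit version for everyone (3.12.2).

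**Analysis.** SAP 7.8 summarises the Baseline version at screening and the last-visit version over the post-baseline period.

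**The concern.** Safety is the primary objective, suicidality is a named safety endpoint, and Protocol 1.4.3 says that precautionary measures were added while psychiatric events are monitored. The rule that decides who enters on suicidality grounds should therefore read the same wherever a site meets it.

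Two things follow if it does not. First, a site that takes the screening bar from 7.8.1, the section describing the scale, could admit a patient with a score of 3. That patient would breach 4.2 i and would already meet a discontinuation criterion. Protocol 4 and 11.1.2 grant no waivers and treat enrolment against key eligibility criteria as a protocol violation.

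Second, criterion i asks a lifetime question, while for some patients the protocol permits a form whose name implies a shorter look-back. The planned screening summary also takes no data from that form.

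**Working it through.** No arithmetic applies. The protocol states no figure that depends on this rule, and the sample size has no statistical basis (Protocol 9.1). The check sets the texts side by side.

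**Step 1: entry outcome by screening C-SSRS ideation score**

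| Score | 4.2 i | 7.8.1 entry sentence | On-study rule (3.10.1, 7.8.1) |
|---|---|---|---|
| 0–2 | not excluded | not excluded | not met |
| 3 | excluded | not named as ineligible | met |
| 4 | excluded | ineligible | met |
| 5 | excluded | ineligible | met |

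The entry texts differ at exactly one score, 3. The lower bound of the discontinuation rule coincides with that of 4.2 i, not with that of the 7.8.1 entry sentence. Section 7.8.1 therefore carries two different cut-offs, one for entry and one for stopping treatment.

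**Step 2: form at screening by entry route**

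| Route | Table 1 footnote l and 3.12.1 | 7.8.1 | Agree? |
|---|---|---|---|
| PRIDE-HD, gap under 3 months | Since Last Visit permitted | Baseline | no |
| PRIDE-HD, gap 3–6 months | screening/baseline | Baseline | yes |
| PRIDE-HD, gap over 6 months (case by case, 4.1 a) | no version stated | Baseline | silent against stated |
| Open-HART | no version stated | Baseline | silent against stated |

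**Step 3: can the lifetime item in 4.2 i be answered on the short-gap route?** The C-SSRS forms are not reproduced in the documents. Judging by its name, the Since Last Visit version covers an interval and would not by itself establish behaviour at any earlier time. Visit 2 repeats that version, so it adds no lifetime answer. On this route psychiatric history need not be entered again if unchanged (3.12.1), and no passage tells the site to consult the C-SSRS answers from the parent study.

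Five other checks do not depend on the C-SSRS version:
- past adverse events of suicidal ideation or attempt, and the investigator's opinion of suicide risk (both in 4.2 i);
- the outright exclusion of suicidality events in inclusion b;
- PBA-s at Visits 1 and 2, with the PBA-s threshold in 4.2 i;
- psychiatric history review at Visit 1.

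They narrow the gap but do not replace an answer to the behaviour item.

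**Step 4: where does a screening Since Last Visit record go in the SAP?** It is not the Baseline version, so it is not in the screening summary of SAP 7.8. It is not post-baseline, so it is not in the other summary either. Such a patient has no screening C-SSRS in any planned table.

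**The case against.** The strongest reply on the threshold is that the rules can be applied together. Section 7.8.1 says that a 4 or 5 is ineligible; it does not say that a 3 is eligible. Section 4.2 excludes anyone meeting any listed criterion, sites review those criteria at both Visit 1 and Visit 2, and 7.8.1 itself shows the lower cut-off for discontinuation. This stands. A reader might infer that 7.8.1 opens the study to a score of 3. The documents do not support that, because 4.2 i excludes a 3 whatever 7.8.1 says. What remains is an eligibility sentence that misstates the threshold.

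On the form, a reader might infer that past behaviour cannot be determined for the typical patient, or that short-gap patients are screened only on their last few weeks. Neither is shown. The Since Last Visit form is permitted, not required. Screening may coincide with the PRIDE-HD follow-up visit, but no share of patients is given. The short look-back is inferred from the form's name. Patients keep their PRIDE-HD subject number, so the design plainly leans on parent-study records, although what those records hold on lifetime suicidality is not in these documents. The checks listed in the working also apply to everyone.

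Finally, the study is single-arm and descriptive, so any effect of mixed screening on post-entry suicidality counts is unquantified. That also stands, and no such effect is claimed.

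**Conclusion.** The inconsistency is real and lies in current operative text. The threshold conflict is confined to one score, 3. The form conflict is confined to PRIDE-HD patients with a gap under 3 months; in addition, Table 1 and 3.12.1 are silent for Open-HART patients and for gaps over 6 months. The consequences are a risk of enrolment in breach of 4.2 i, a lifetime item that the permitted form may not answer alone, and an incomplete screening summary under SAP 7.8. There is no effect on sample size or power. The documents give neither the prevalence of a score of 3 or of past behaviour, nor the share of patients on each route, so the number affected cannot be stated.

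The conclusion on the lifetime item assumes that the Since Last Visit form covers only the interval its name describes. A second caution concerns versions: the SAP plans for up to 650 patients and the protocol for up to 300, so the SAP appears to follow a later amendment that is not among the documents. If that amendment already reconciles these sections, only the SAP alignment needs checking.

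Given the explicit exclusion in 4.2 i and the overlapping safeguards, this should be fixed rather than being a fatal defect.

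**What to change.** Three wording changes:

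1. Reconcile the synopsis, 4.2 i and 7.8.1 so that one C-SSRS screening threshold is stated, and check it against the discontinuation rule in 3.10.1 and 7.8.1.
2. Reconcile Table 1 footnote l, 3.12.1 and 7.8.1 on the screening form, so that the lifetime behaviour item in 4.2 i can be answered for every entry route, including Open-HART and gaps over 6 months. Correct the visit number in 7.8.1 at the same time.
3. Align the screening summary in SAP 7.8 with the form actually used, so that no treated patient is silently absent from it.

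This review does not say which threshold or which form is right; that is for the sponsor's clinical team.

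The cost is amendment wording and possibly a few more screen failures. The C-SSRS is already given at screening, so no visit is added.

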7.9. Methods and Timing of Assessing, Recording, and Analyzing Safety Data

All adverse events will be reviewed on a periodic basis by the clinical project physician/medical monitor according to the safety monitoring plan (eg, scheduled safety reviews for pridopidine) as interim/preliminary safety databases become available. Safety data will additionally be evaluated periodically and ad hoc (if necessary) in the Product Safety Group.

Methods and timing of assessing safety data are discussed in Section 3.12. Procedures for recording safety data are discussed in Section 13.1 and methods of analyses are discussed in Section 9.7.2.

Information about the DSMB used for this study is provided in Section 3.6.1.

**8. ASSESSMENT OF PHARMACOKINETICS/
PHARMACODYNAMICS BIOMARKERS/
PHARMACOGENOMICS/ IMMUNOGENICITY**

Pharmacokinetics is not evaluated in this open-label study. Pharmacokinetic samples will be aimed to be drawn, to the extent possible, in the event of a SAE, an AE leading to discontinuation, or for patients who withdrew prematurely because of lack of efficacy.

Pharmacodynamics, pharmacogenomics, or immunogenicity will not be assessed in this open-label study.

9. STATISTICS

This section describes the statistical analysis as foreseen at the time of planning the study. Changes, additions, and further details about the analyses will be described in the statistical analysis plan. After finalization of the statistical analysis plan, any additional analyses or changes to analyses that may be required will be fully disclosed in the clinical study report.

9.1. Sample Size and Power Considerations

This is an open-label study. The sample size for this study is not based on statistical considerations; hence, only descriptive statistics will be presented. Up to 300 subjects who completed the PRIDE-HD or transitioned from the ongoing Open-HART study and met patient exclusion/inclusion criteria will be enrolled.

9.2. Analysis Sets

9.2.1. Intent-to-Treat Analysis Set

The intent-to-treat (ITT) analysis set will include all enrolled patients, regardless of whether or not a patient took any study drug. A patient is considered enrolled according to the status reported in the database.

9.2.2. Safety Analysis Set

The safety analysis set will include all patients who receive at least 1 dose of study drug.

9.2.3. Full Analysis Set

The full analysis set will include all patients in the ITT population who receive at least 1 dose of study drug and have at least 1 post-baseline efficacy assessment.

9.3. Data Handling Conventions

For all variables, only the observed data from the patients will be used in the statistical analyses, i.e., there is no plan to estimate missing data.

9.4. Study Population

The ITT analysis set (see Section 9.2) will be used for all study population summaries unless otherwise noted. Summaries will be presented for all patients.

9.4.1. Patient Disposition

Data from patients in the ITT, safety, and full analysis sets will be summarized using descriptive statistics. Data from patients who withdraw from the study will also be summarized by reason for withdrawal using descriptive statistics.

9.4.2. Demographic and Baseline Characteristics

Patient demographic and baseline characteristics, including medical history, prior medications, and ECG findings will be summarized using descriptive statistics. For continuous variables, descriptive statistics (number [n], mean, standard deviation [SD], median, minimum, and maximum) will be provided. For categorical variables, patient counts and percentages will be provided. Categories for missing data will be presented if necessary.

9.5. Efficacy Analysis

9.5.1. Efficacy Endpoint

Efficacy measures and time points are provided in Section 3.3 and in Table 1.

9.5.2. Planned Method of Analysis

The full analysis set (see Section 9.2) will be used for all efficacy analyses.

No formal inferential statistics will be applied to the efficacy endpoints. Efficacy analyses will be considered exploratory and will include descriptive statistics. Comparisons will generally be made to baseline, as appropriate. Descriptive statistics over time will be presented to detect trends via changes from baseline.

9.6. Multiple Comparisons and Multiplicity

Not applicable.

9.7. Safety Endpoints and Analysis

Safety analyses will be performed on the safety analysis set (see Section 9.2).

9.7.1. Safety Endpoints

Safety measures and time points are provided in Section 3.4 and in Table 1.

9.7.2. Safety Analysis

All adverse events will be coded using the Medical Dictionary for Regulatory Activities (MedDRA). Each patient will be counted only once in each preferred term or SOC category for the analyses of safety. Summaries will be presented for all adverse events (overall and by severity), adverse events determined by the investigator to be related to study treatment (i.e., reasonable possibility; see Section 7.1.4) (defined as related or with missing relationship) (overall and by severity), SAEs, and adverse events causing withdrawal from the study. Summaries will be presented by treatment group and for all patients. Patient listings of SAEs and adverse events leading to withdrawal will be presented.

Changes in laboratory and vital signs measurement data will be summarized descriptively. All values will be compared with prespecified boundaries to identify potentially clinically significant changes or values, and such values will be listed.

The use of concomitant medications will be summarized by therapeutic class using descriptive statistics. Concomitant medications will include all medications taken while the patient is treated with study drug.

For continuous variables, descriptive statistics (n, mean, SD, median, minimum, and maximum) will be provided for actual values and changes from baseline to each time point. For categorical variables, patient counts and percentages will be provided. Descriptive summaries of SAEs, patient withdrawals due to adverse events, and potentially clinically significant abnormal values (clinical laboratory or vital signs) based on predefined criteria will also be provided.

If any patient dies during the study, a listing of deaths will be provided and all relevant information will be discussed in the patient narrative included in the clinical study report.

